- 8. Physical examination includes height and weight, evaluation of the neck/thyroid, chest/lung, heart, lymph nodes, abdomen, nervous system, etc. Body height is measured only at the screening visit. A complete physical examination (except height measurement) is performed at screening and on Day 1, 28 ±3, 84 ± 5, and 112 ±7. At other visits, only the body weight needs to be measured.
- 9. Nervous system physical examination is required for each visit, and the investigators should actively query about nervous system symptoms such as cephalgia, convulsions, confusion, vision loss, speech disturbances, facial drooping, weakness, problems with coordination, gait and sensory loss, and mental impairment. If any of the above symptoms appear, a neurology consult would be ordered for further assessment, and extra examinations including CT scanning, MRI examination and other related tests will be conducted by neurologists' judgment.
- 10. At screening visit, if pulmonary function tests show FEV1 or FVC < 70% of normal predicted value, the subject needs to be excluded.
- 11. Dermatology examination includes an overall examination of the skin for lesions and examinations of the extremities. It is mainly aimed at excluding suspected lesions of basal cell carcinoma. Dermatology examinations at screening and on day 84 ± 5 (12 weeks) visits need to be performed in the department of dermatology. Dermatology examinations at other visits can be performed by the investigator.
- 12. Ophthalmologic examination includes checking of visual abnormalities (for example, blurred vision or decreased visual acuity) in subjects and needs to be performed in the department of ophthalmology.
- 13. In case optical coherence tomography (OCT) shows suspected macular edema, it is required to perform a complete retinal examination including collecting history of eye diseases, visual acuity check, and dilated fundus examination. During the study, if an ophthalmologic examination identifies visual abnormalities (e.g., blurred vision or decreased visual acuity), then, additional OCT can be performed. All subjects diagnosed with macular edema must discontinue the investigational product.
- 14. On Day 1, 5 and 8, hematology tests need to be performed before administration and at 4-6 hours after administration respectively. At other visits during treatment, only hematology tests prior to administration need to be performed.

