- 21. Collection of PK blood samples only applies to subjects in the PK subgroup. Time points for the collection of PK blood samples: 15-30 min before administration and 4-6 hours after administration at week 1 (day 1 and day 5), week 2 (day 8), week 4 (day 28), week 8 (day 56), and week 12 (day 84); 1-2h after administration at week 1 (day 1 and day 5) and week 4 (day 28).
- 22. The subjects in the PK subgroup are required to undergo measurement of lymphocyte counts (used for investigating the PD) at all time points for the collection of PK blood samples. According to the study flow chart, if there are corresponding hematology tests at the time points for the collection of PK blood samples, such as time points before administration and at 4-6 hours after administration on day 1, it is not necessary to collect additional PD blood samples, otherwise it is required to collect PD blood samples simultaneously. For the subjects in the non-PK subgroup, lymphocyte counts used for the PD study are obtained from hematology tests, so it is not necessary to collect additional PD blood samples.
- 23. Mayo score: The complete Mayo score is calculated from the stool frequency, rectal bleeding, endoscopic findings, and physician overall evaluation. See section 7.2.3. The adapted Mayo score is calculated from stool frequency, rectal bleeding, and endoscopic findings, See Section 7.2. Partial Mayo scores will be calculated based on the data of item 1, 2 and 4 in Section 7.2. (stool frequency, rectal bleeding, endoscopic findings,).
- 24. Subject diaries are dispensed at screening visits and reviewed at all visits from baseline to last dose/early termination from the study.
- 25. IBDQ will be completed by subjects at baseline and week 12 visits.
- 26. Subjects who complete the 12 weeks of study stage 1 but do not enter the study stage 2 or early withdraw from the study will undergo safety follow-up for 4 weeks after the last dose.

Protocol No.: CBP-307CN002 Confidential

Table 3. Sub-study 1 of the Study Stage 2: Study Flow Chart for the Entry of Subjects into Double-Blind Maintenance Treatment After Achieving Clinical Response at Week 12

Study Plan	Stage 2 Screening ¹	Sub-stu	dy 1 of the Study	Last dose/early Termination	Follow-up			
	Week 13	Week 18	Week 24	Week 32	Week 40	Week 48	Week 52	
Visit No. ²	12	13	14	15	16	17	18	
Day	Day 90 ±5 1	Day 126 ±5	Day 168 ±5	Day 224 ±5	Day 280 ±5	Day 336 ±5	Day364 ±5	
Informed Consent ³	X							
Inclusion/exclusion criteria	X							

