6.2. BASELINE

For stage 1: Unless otherwise specified, baseline is defined as the last non-missing measurement taken prior to the first treatment date (including unscheduled assessments) in stage 1. In the case where the last non-missing measurement and the reference start date coincide, and no time collected, that measurement will be considered pre-dose, except that the protocol specifies the measurement is post-dose.

For subject randomized but not treated, baseline is defined as the last non-missing measurement on or before randomization date.

For subjects entered into stage 2 sub-study 1: the baseline will be the same as in stage 1.

For subjects entered into stage 2 sub-study 2: the baseline is defined as the last non-missing measurement taken prior to the first treatment date (including unscheduled assessments) in stage 2 sub-study 2.

For all stages (0.2mg only) analysis, baseline will be the same as in stage 1.

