6.3. RETESTS, UNSCHEDULED VISITS

In general, for by-visit summaries, data recorded at the nominal visit will be presented. Unscheduled measurements will not be included in by-visit summaries but will contribute to the minimum, maximum, best or worst case value where required (e.g. shift table).

Unless otherwise specified, in the case there are more than one records in the same visit, the latest available measurement for that visit will be used for by-visit summaries.

Listings will include scheduled, unscheduled, retest data.

Document: Statistical Analysis Plan

Author: [name]

Version Number: 1.1

Version Date: 18Jan2023

Template No.: CS_TP_BS016 Revision 5

Reference: CS_WI_BS005

Effective Date: 01Apr2018

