3. If urinalysis show occult blood or abnormal urine protein in subjects' urine samples, a microscopy needs to be performed. A microscopy mainly refers to a blood test that measures

Document: Statistical Analysis Plan

Author: [name]

Version Number: 1.1

Version Date: 18Jan2023

Template No.: CS_TP_BS016 Revision 5

Reference: CS_WI_BS005

Effective Date: 01Apr2018

white blood cells and red blood cells. All other tests are tests with test strips.

4. Fecal culture/microscopy (involving fecal culture, C.difficile, eggs and parasites) is required to be performed at screening. During the screening period and any time point during the study if the subject has symptoms including aggravation of the disease condition or disease activity before recovery, stool samples can be collected for fecal culture/microscopy and C.difficile analysis.
5. Women with fertility are required to undergo a pregnancy test (involving blood β -human chorionic gonadotropin and urine pregnancy test). At screening, subjects with amenorrhea for <5 years are required to undergo measurement of follicle stimulating hormone to confirm postmenopausal condition.
6. Subjects can be enrolled in the study if it is evidenced that TB was treated successfully and Quantiferon or Quantiferon Plus test result is negative. If Quantiferon or Quantiferon Plus test result was uncertain at screening, the retest may be carried out during screening period. If Quantiferon or Quantiferon Plus retest result was uncertain, the subject should not participate in the study. If Quantiferon or Quantiferon Plus retest result is negative, the subject can be enrolled in the study.

Hematology, blood chemistry, and coagulation test results will be summarized at each study visit by treatment group.

Subjects with abnormalities in hematology assessments, defined as absolute lymphocyte count (ALC) <200 cells/uL, absolute neutrophil count (ANC) < 500 cells/uL as well as ANC <1000 cells/uL and total WBC >20,000 cells/uL will be summarized for each treatment group.

In addition, the change and percent change from baseline in complete blood count with Differential will be summarized for each treatment group.

The incidence of subjects with abnormalities for ALT/AST/ALP will be summarized overall and at each visit for each treatment group for the following categories:

$\geq 3 \times \text{ULN}$

$\geq 5 \times \text{ULN}$

Document: Statistical Analysis Plan

Author: [name]

Version Number: 1.1

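### As written, the by-visit hematology rows are post-dose on Days 1, 5 and 8 and pre-dose from Day 15, so sampling time is confounded with time on treatment in the lymphocyte summary

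*SAP*

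**What the plan says.** **Sampling.** Protocol Table 2 note 14 reads: "On Day 1, 5 and 8, hematology tests need to be performed before administration and at 4-6 hours after administration respectively". It continues: "At other visits during treatment, only hematology tests prior to administration need to be performed". Table 2 marks hematology on Days 1, 5, 8, 15, 28, 42, 56, 70 and 84 of Stage 1 treatment.

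**Summary.** SAP 15.3 says: "Hematology, blood chemistry, and coagulation test results will be summarized at each study visit by treatment group". For the differential count it adds: "In addition, the change and percent change from baseline in complete blood count with Differential will be summarized for each treatment group". Neither sentence separates pre-dose from post-dose samples.

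**Choice of record.** Under SAP 6.3, when one visit holds more than one record, "the latest available measurement for that visit will be used for by-visit summaries", unless otherwise specified. Nothing in SAP 15.3 specifies otherwise.

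**Baseline.** Under SAP 6.2, "baseline is defined as the last non-missing measurement taken prior to the first treatment date (including unscheduled assessments) in stage 1". Baseline is therefore a pre-dose value.

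**Pharmacokinetic (PK) subgroup.** Under Table 2 note 22, these subjects are "required to undergo measurement of lymphocyte counts (used for investigating the PD) at all time points for the collection of PK blood samples". Note 21 and protocol 7.4.1 place 4-6 h samples at weeks 4, 8 and 12 as well as on Days 1, 5 and 8. The SAP does not say whether the extra lymphocyte counts enter the hematology table.

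**The concern.** A latest-record rule suits retests, where the later value replaces a doubtful one. Here it meets two planned samples that answer different questions, and it discards the pre-dose one at exactly three visits, all early.

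For most analytes a few hours make little difference. Lymphocytes are the exception for this drug. Protocol 3.4.2 puts the maximal fall after a single dose at about 6 h, so a 4-6 h count lies near the low point and a pre-dose count lies at the trough. A reader who follows the lymphocyte rows down the table sees time on treatment and sampling time change together between Day 8 and Day 15 and cannot separate them.

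The dose also steps up on two of the three days. Under protocol Table 5, in the 0.2 mg arm, the Day 5 pre-dose count follows 0.05 mg and the Day 8 pre-dose count follows 0.1 mg. The post-dose counts on those days follow the first 0.1 mg and the first 0.2 mg dose. The choice of record therefore also decides which dose the row describes.

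**Working it through.** **1. Check the sampling schedule against the plan's own figure.** Protocol 7.4.1 gives 3 mL per PK sample and about 45 mL in total.
- Six visits (Days 1, 5, 8, 28, 56, 84) with a pre-dose and a 4-6 h sample: 6 × 2 = 12.
- Three 1-2 h samples (Days 1, 5, 28): 3.
- Total: 12 + 3 = 15 samples, and 15 × 3 mL = 45 mL. This reproduces the stated volume and confirms 4-6 h samples at weeks 4, 8 and 12.

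**2. Apply the SAP 6.3 rule visit by visit.**

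| Visit | Scheduled hematology | Record kept | PK subgroup, if its extra counts are pooled |
|---|---|---|---|
| Days 1, 5, 8 | pre-dose and 4-6 h | post-dose | post-dose |
| Day 15 | pre-dose | pre-dose | pre-dose |
| Day 28 | pre-dose | pre-dose | post-dose |
| Day 42 | pre-dose | pre-dose | pre-dose |
| Day 56 | pre-dose | pre-dose | post-dose |
| Day 70 | pre-dose | pre-dose | pre-dose |
| Day 84 | pre-dose | pre-dose | post-dose |

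On scheduled hematology alone, the basis changes once, between Day 8 and Day 15. If the PK-subgroup counts are pooled (about 90 subjects, against about 134 randomized), the rows for weeks 4, 8 and 12 also mix post-dose subjects with pre-dose subjects.

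**3. Direction, by illustration.** Assume one compartment, a peak at 5 h (the protocol gives 4-6 h), and a half-life of either 25 h (protocol 3.4.1) or 37.7 h. The second value is implied by the AUC accumulation ratio of 2.8: k = −ln(1 − 1/2.8)/24 = 0.0184 per h, and ln 2/k = 37.7 h. Sum the doses by superposition, C(t) = Σ dose × ka/(ka − ke) × (e^(−ke·Δt) − e^(−ka·Δt)). For the 0.2 mg schedule, as a share of the week 12 trough:
- Day 8 pre-dose: 0.42 to 0.46
- Day 8 at 5 h: 0.88 to 1.19
- Day 15 pre-dose: 0.97 to 0.99

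These are concentrations, not counts. They show that the two Day 8 samples are taken at concentrations that differ by a factor of about 2.1 to 2.6.

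**4. Can the size in lymphocytes be computed?** Try a sigmoid effect curve fixed by two phase I figures for 0.25 mg: a 40% fall at about 6 h after a single dose, and 75% pre-dose at steady state. Take accumulation of 3, so k = ln(1.5)/24, and a peak at 5 h.
- The steady-state trough relative to the single-dose peak is e^(5k) × (1/1.5)/(1 − 1/1.5) = 1.088 × 2 = 2.18.
- The effect odds rise from 0.40/0.60 = 0.667 to 0.75/0.25 = 3, a ratio of 4.5. The Hill exponent is ln 4.5/ln 2.18, about 1.93.

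Now test the curve on protocol figures that were not used to fit it:
- Single 2.5 mg: odds 0.667 × 10^1.93 = 56.7, a 98% fall. Protocol 3.4.2 reports about 77%.
- 0.1 mg pre-dose at steady state: odds 3 × 0.4^1.93 = 0.51, a 34% fall. Protocol 5.2.2 reports about 50%.
- Implied half-life: 24 × ln 2/ln 1.5 = 41 h. Protocol 3.4.1 states about 25 h.

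The curve misses the plan's own data, so its Day 8 percentages cannot be used as estimates.

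**The case against.** The strongest reply is that little depends on this table. SAP 15 makes safety summaries descriptive, with no statistical comparisons. The SAP defines no onset endpoint and leaves pharmacokinetics and pharmacodynamics to a separate plan. Placebo follows the same sampling schedule, so drug and placebo are compared like for like within each visit. Worst-value and shift outputs do not use the latest-record rule. SAP Appendix 1 says outputs follow table shells, which are not among the documents and may already show time points separately.

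Most of this stands and limits the point. Two parts do not remove it. Like-for-like rows do not give a like-for-like series: the drug-placebo difference itself moves from a near-nadir to a trough basis between Day 8 and Day 15. And the shells might split the time points, but the SAP text does not require it, and its stated rule points the other way.

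A reader might go further in four ways that the documents do not support:
- **That the table misstates onset.** No onset analysis is defined. A misleading impression is possible but not shown.
- **That the Day 8 effect is overstated by about 30 points.** The curve in step 4 of the working would suggest a gap of that order, but it fails against the protocol's own figures. The post-dose count is also a real count after the first 0.2 mg dose, not an inflated version of the pre-dose one.
- **That the rule breaks comparison with the 50% and 70% falls behind dose selection.** Those are pre-dose, steady-state values. Days 1 to 8 fall within titration and could not match them on either basis, while scheduled hematology from Day 15 is already pre-dose.
- **That PK and non-PK subjects will be mixed at weeks 4, 8 and 12.** This depends on whether the extra counts enter the hematology table, which the SAP leaves open.

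**Conclusion.** The point holds in limited form. Read together, Table 2 note 14, SAP 6.3 and SAP 15.3 put the by-visit hematology rows on a post-dose basis on Days 1, 5 and 8 and on a pre-dose basis from Day 15. For lymphocytes, this confounds sampling time with time on treatment and can make the fall look earlier or larger by Day 8. A stated rule discards planned samples here, so this is more than a missing detail.

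The direction rests on the protocol's statement that the single-dose fall is greatest at about 6 h. The size in lymphocyte counts cannot be obtained from the documents. The conclusion assumes that the shells follow the SAP text. Mixing within the rows for weeks 4, 8 and 12 is conditional on pooling the PK-subgroup counts. The primary and secondary efficacy analyses are untouched.

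**What to change.** In SAP 15.3, exempt hematology from the latest-record rule of SAP 6.3 and state that:
- Post-baseline by-visit rows use the pre-dose sample in all subjects. The Day 1 pre-dose sample precedes the first dose and is not an on-treatment value, so Day 1 appears only as a post-dose row.
- The 4-6 h samples on Days 1, 5 and 8 appear in separate, labelled post-dose rows.
- The extra lymphocyte counts from the PK subgroup are either included or not. If they are, their post-dose values appear only in separate rows.
- All samples stay in the worst-value, shift and ALC <200 cells/uL tables.

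The cost is one SAP sentence and a few extra table rows. No additional sampling is needed.

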15.4. ECG EVALUATIONS

The following ECG parameters will be reported for this study:

- Heart Rate (bpm)
- PR Interval (msec)
- RR Interval (msec)
- QRS Interval (msec)
- QT Interval (msec)
- QTcF Interval (msec)
- Overall assessment of ECG (Investigator's judgment):
 - Normal
 - Abnormal, Not Clinically Significant (NCS)
 - Abnormal, Clinically Significant (CS)
 - Not Evaluable

The following summaries will be provided for ECG data:

- Actual value and change from baseline by visit
- Shift from baseline to worst post baseline for overall evaluation
- Incidence of subjects with abnormalities for QT Internal/QTcF by visit
- Shift from baseline according to post-baseline maximum value category for QT Interval

Document: Statistical Analysis Plan

Author: [name]

Version Number: 1.1

Version Date: 18Jan2023

Template No.: CS_TP_BS016 Revision 5

Reference: CS_WI_BS005

Effective Date: 01Apr2018

and QTcF

- Shift from baseline according to post-baseline maximum increase category for QT Interval and QTcF
- Listing of ECG
- Listing of Holter ECG

15.4.1. ECG MARKEDLY ABNORMAL CRITERIA

Markedly abnormal quantitative ECG measurements will be identified in accordance with the following predefined markedly abnormal criteria:

- Absolute values for QT interval and QTcF will be classified as:
 - > 450 msec
 - > 480 msec
 - > 500 msec
- Change from Baseline for QT interval and QTcF will be classified as:
 - >30 msec increase from baseline
 - >60 msec increase from baseline

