7.5. Monitoring of adverse events of special interest

During the study on CBP-307, AEs caused by S1P1 receptor stimulation that were found in previous clinical studies on other similar drugs will be closely monitored. These AEs include:

- a. Bradycardia and cardiac conduction abnormalities: It was reported that the adverse reactions caused by the first dose of similar drugs mainly included reversible bradycardia, first grade atrioventricular block and sinus arrest. Reduced heart rate is an expected adverse reaction to S1P1 agonists. These negative chronotropic effects of S1P1R agonists appear to attenuate over time after S1PR desensitization and internalization into cardiac myocytes. This effect appears to occur with increasing exposure to study drug; thus, gradual titration of the dose of CBP-307 within 1 week may mitigate against larger reductions in heart rate.
- b. Pulmonary toxicity: An initial sharp decrease followed by slow progressive decline over time in FEV₁ was observed in clinical studies of the same category of drugs. In this study, FEV₁ and FVC in all subjects will be measured; DLCO will be measured in sites that are equipped with the right facilities. Each subject with abnormal pulmonary function test results will be followed up. If the subject's pulmonary function test results (FEV₁ and/or FVC) fall below 50% of the predicted values, treatment should be discontinued immediately, and appropriate clinical follow-up (for at least 3 months) should be performed until the resolution is confirmed or no further aggravation is expected by investigator.
- c. Hepatotoxicity: fingolimod caused frequent, reversible liver enzyme elevations greater than 3-fold above the ULN in up to 12% of patients. In the completed phase I clinical study on CBP-307, ALT levels slightly increased in individual subjects but were all below 3 times the ULN; and this side effect was also milder than that of fingolimod. In this study, blood chemistry analysis will include measurement of LFT levels. Subjects with abnormal LFT levels will be continuously followed up until the LFT values returns to the normal/baseline level.

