6. GENERAL CONSIDERATIONS

Analysis results will be presented using descriptive statistics. For categorical variables, the number and percentage of subjects in each category will be presented; for continuous variables, the number of subjects [n], mean, standard deviation [SD] or standard error [SE], median, minimum, and maximum will be presented. Statistical comparisons will be tested at two-sided alpha of 0.05 significance level, unless otherwise specified. Data collected in the study will be presented in by-subject listings for all subjects in the full analysis set (efficacy analysis) and safety analysis set

Document: Statistical Analysis Plan

Author: [name]

Version Number: 1.1

Version Date: 18Jan2023

Template No.: CS_TP_BS016 Revision 5

Reference: CS_WI_BS005

Effective Date: 01Apr2018

(safety analysis), unless otherwise specified. All by subject listings will be presented by treatment group, subject identification number in ascending order, unless otherwise specified.

For stage 1 analysis, the analysis period for subjects who enroll stage 2 will be from screening (baseline visit) in stage 1 until before the first dose of stage 2. And for subjects who will not enroll stage 2 (including screen failed subjects before randomization, randomized subjects but not treated, and subjects early discontinued in stage 1), the analysis period will be from screening (baseline visit) in stage 1 until end of study in stage 1. For stage 2 sub-study 1 analysis, the full/safety analysis population will be the randomized subjects who receive at least one dose of study medication or placebo in stage 2, but the analysis period will be from screening (baseline visit) in stage 1 until the end of study in stage 2. But for subjects who will enroll stage 2 sub-study 2, the analysis period will be the date of first dose of the open-label CBP307 0.2mg in stage 2 until the end of study in stage 2 since treatment is changed to open-label CBP307 0.2 mg QD.

For 0.2mg (all stages) group, the analysis period will be the date of first dose of initial administration until the end of stage 2 study, including stage 2 sub-study 1 and stage 2 sub-stage 2.

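### The SAP has no PR-interval category, so asymptomatic first-degree AV block that is not reported as an adverse event is not counted by treatment group

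*SAP*

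**What the plan says.** SAP 15.4 lists PR among the ECG parameters to be reported. The outputs that follow treat the parameters differently.

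- All continuous parameters get "Actual value and change from baseline by visit". Under SAP 6 such a summary gives n and "mean, standard deviation [SD] or standard error [SE], median, minimum, and maximum will be presented".
- Per-subject incidence is planned only as "Incidence of subjects with abnormalities for QT Internal/QTcF by visit". Both category shift tables (maximum value, maximum increase) are also tied to QT and QTcF.
- The one other shift table is "Shift from baseline to worst post baseline for overall evaluation", which uses the investigator's grading of the whole ECG.
- ECG and Holter data are listed by subject.

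SAP 15.4.1 then defines the markedly abnormal classes. The absolute classes open with "Absolute values for QT interval and QTcF will be classified as" (limits 450, 480 and 500 msec). The change classes open with "Change from Baseline for QT interval and QTcF will be classified as" (limits 30 and 60 msec). PR has neither.

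Protocol 7.5, item a, says the reactions reported after a first dose of similar drugs were mainly "reversible bradycardia, first grade atrioventricular block and sinus arrest". SAP 15.1.5 includes bradycardia and conduction abnormality among the adverse events of special interest and plans a table by SOC and PT.

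**The concern.** Slowed AV conduction is a finding in individual subjects, and PR is the ECG measurement that shows it. For a risk that the protocol itself names, a reader of the safety report would want to know how many subjects in each arm went from a normal to a prolonged PR. SAP 15.5 already answers that kind of question for bradycardia, the reaction named beside first-degree block in Protocol 7.5, because low heart rate is a markedly abnormal class with its own incidence row. First-degree block has no such row, although the data are collected at every 12-lead ECG.

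At stake is the completeness of the safety description. No efficacy result depends on it.

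**Working it through.** The plan states no figure on this point, so the main check is a comparison of the planned outputs.

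**1. Could any planned output count subjects with new PR prolongation by arm?**

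- By-visit PR summary (SAP 15.4 with SAP 6): no. It gives location, spread and range. The maximum change shows the largest rise in an arm at a visit but not how many subjects had a rise. The maximum absolute value need not be new either, because the cardiac exclusions in Protocol 5.4.1 (item 17e) name second- and third-degree block but not first-degree.
- Incidence and category shift tables (SAP 15.4, 15.4.1): no, QT and QTcF only. The interim list in SAP 4.2 is worded more loosely for the shifts to maximum, but SAP 15.4 restricts them to QT and QTcF.
- Overall-assessment shift (SAP 15.4): no. A move from normal to abnormal does not say which interval changed.
- TEAE and special-interest tables (SAP 15.1.1, 15.1.5): only for events that investigators report. Protocol 8.1.1 lists ECG findings that change medical care among the things that are adverse events. The examples in Protocol 8.3 are Mobitz II block, third-degree block and other significant conduction abnormality, without first-degree.
- ECG and Holter listings: every value is there, but the reader must count by hand with no pre-set criterion.

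**2. Which PR values enter the by-visit summary?**

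SAP 6.3 leaves unscheduled measurements out of by-visit summaries and lets them contribute only where a minimum, maximum, best or worst value is required, giving a shift table as its example. PR has no shift table. An unscheduled ECG, for example one taken during the extended monitoring after 6 hours in Protocol 6.2.1, is therefore left out of the by-visit PR summary.

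SAP 6.3 also keeps the latest record when a visit has more than one. Protocol Table 2 (note 5) schedules ECGs before dosing and at 4 and 6 hours on days 1, 2, 5 and 8. The SAP does not say that these time points are summarised separately. If they are treated as one visit, the 6-hour value replaces the 4-hour value, and a 4-hour peak drops out of the maximum as well as the mean. Protocol 3.4.4 puts the fall in heart rate at 2 to 4 hours after dosing; it gives no time course for PR.

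**3. Illustration of what a mean can hide**

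From the documents: 52 subjects per group (SAP 7.4). Assumed, not in the documents: 3 subjects on 0.2 mg gain 60 ms of PR and the others none; the SD of the PR change is 15 to 20 ms.

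- Shift in the arm mean = 3 × 60 / 52 = 3.46 ms.
- Standard error of the between-arm difference = SD × √(2/52): 15 × 0.196 = 2.94 ms, or 20 × 0.196 = 3.92 ms.
- Ratio = 3.46 / 3.92 = 0.9 to 3.46 / 2.94 = 1.2.
- Category row = 3/52 = 5.8%.

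Varying the assumed rise for the same 3 subjects, 30 ms gives 3 × 30 / 52 = 1.7 ms and 80 ms gives 3 × 80 / 52 = 4.6 ms. For one subject the shifts are 30 / 52 = 0.6 ms and 80 / 52 = 1.5 ms.

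SAP 15 plans no statistical comparison of safety data, so the standard error is only a yardstick for how noticeable such a shift would be.

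**The case against.** The strongest reply is that PR is already well covered. Median, minimum and maximum are planned; in the illustration a 60 ms rise would normally set the maximum change. The listings hold every value, so a count can be made at any time. More serious conduction problems are caught elsewhere: new second-degree or worse block at 6 hours prolongs monitoring (Protocol 6.2.1), and significant conduction abnormalities are reported as events of special interest (Protocol 8.3). All of this stands, and it confines the gap to asymptomatic first-degree block that nobody reports as an adverse event.

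Three stronger readings are tempting, and the documents do not support them.

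- A reader might infer that PR is visible only as a mean change. The range, the listings, the overall-assessment shift and the adverse event tables rule that out.
- A reader might infer from Protocol 8.1.1 that asymptomatic PR prolongation cannot be an adverse event unless care changes. That item is one entry in an inclusion list; the same section accepts an abnormal test finding as an adverse event, and grade 1 in Protocol 8.1.2 covers asymptomatic findings. Such prolongation may be reported, but reporting is not assured.
- A reader might infer that the QT tables are misplaced, since Protocol 3.3.1 rates the QT potential as very low. But QTcF is an entry exclusion and a 6-hour monitoring trigger, so tabulating it is consistent with the protocol. That section also reports no PR effect in dogs.

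The existing routes still do not give a count by arm against a criterion fixed in advance, and SAP 6.3 weakens the maximum as a safeguard.

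**Conclusion.** The gap is real but narrow. No planned table counts subjects with newly prolonged PR by treatment group, although first-degree AV block is a named class reaction and conduction abnormality is an event of special interest. First-degree block that is asymptomatic and not reported as an adverse event would have to be found from ranges or listings. Unscheduled ECGs are outside the by-visit PR summaries; whether the 4-hour values are too depends on how the SAP means a visit to be read.

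The size cannot be taken from the documents. The 3-in-52 example rests on an assumed number affected, an assumed rise and an assumed SD, and shows only that a mean by itself can hide a few affected subjects. The primary efficacy analysis and the monitoring rules are not affected. This is a worthwhile, inexpensive improvement to the safety tables.

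**What to change.** Add to SAP 15.4.1, by treatment group: n (%) of subjects with newly prolonged PR (absolute class, among those not prolonged at baseline), and n (%) in classes of PR increase from baseline. Add PR to the shift tables in SAP 15.4, from baseline to worst post-baseline value.

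State that these outputs use all post-dose time points, including unscheduled ECGs, and say whether the by-visit summaries treat the same-day time points separately.

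The documents contain no PR thresholds. The sponsor's clinical team should set the descriptive cut-offs before unblinding.

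The cost is some SAP wording and a few extra descriptive rows. No new data are needed, and no dosing, monitoring or stopping rule changes.
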